13. ETHICAL CONSIDERATIONS

13.1. Ethical Principles

The study will be conducted in accordance with:

- The most recent version of the [World Medical Association Declaration of Helsinki](#) – Ethical Principles for Medical Research Involving Human Participants;
- National Statement on Ethical Conduct in Human Research ([NHMRC 2007a](#), updated May 2015);
- Notes for Guidance on Good Clinical Practice – Annotated with Comments ([CPMP/ICH/135/95](#)), as adopted by the Australian TGA (July 2000); and
- The current Clinical Trial Protocol as approved by the HREC/IRB and the USAMRMC HRPO.

The PI will take care to minimize any discomfort experienced by participants during the study. The only invasive procedures the blood collection by cannulation/venipuncture. The maximum amount of blood to be collected from an individual over the entire study period is approximately 135 mL ([Appendix 3](#)).

Additional blood samples may be taken for safety assessments as required by the PI or at times specified by the sponsor provided the total volume taken during the study does not exceed 140 mL during the study period.

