	
Orlando system).
 
 • After pupil dilation: 
 ○ MAIA microperimetry; ○ Heidelberg Spectralis SD-OCT (including wide field macula scan); ○ Heidelberg Spectralis qFAF (set of 3 images to ensure consistency in measurement); ○ Digital photograph of corneal surface (conventional and wide field); ○ Digital photograph of retina (conventional and wide field); ○ Slit lamp retinal examination and IOP measurement; and • Psychiatric Assessments: 
 ○ M.I.N.I. English Version 7.0.2 at Weeks 12, 24 and 52; ○ DHI (only collected if participant reports AE of dizziness or vertigo); ○ LSEQ; and, ○ C-SSRS – every 4 weeks \pm 1 week after the Week 52 Visit • AEs. 
Part 3 - Follow-up Ongoing AEs Weeks 76, 89, and 104 (Visits 8, 9 and 10) every 3 months until resolution (out to 12 months post final study drug dose – visits will only be scheduled if an AE was ongoing at a prior visit):
 
 • 12-lead ECG • Blood sampling. 
 • CBC and biochemistry; and • MetHb%. • Urinalysis (specific gravity, pH, glucose, protein, blood, ketones, leukocyte esterase, and nitrites). Microscopic examination (if blood, leukocyte esterase or nitrites are positive). • Ophthalmic assessments, including selected ophthalmic examination, microperimetry, BCVA (EDTRS), FM-100 hue testing, Mars letter contrast sensitivity test, M-chart and qFAF to follow only specific, abnormal results. • Psychiatric assessments: 
 ○ M.I.N.I. English Version 7.0.2. (If required to follow-up an AE or disorder). ○ DHI (if AE reported by participant); and • Any other AE. 
For compliance confirmation during the dosage phase – plasma samples will be taken at Weeks 1, 4, 12, 24, and 52. There is no specific timing for obtaining the pharmacokinetic (PK) sample during each scheduled visit. The date and time of the PK sample is to be recorded in the eCRF. Date, time, and number of tablets recorded in participant diary cards and/or electronic compliance management system will also be transferred to the eCRF.
 
Drawing of blood samples is estimated to be 135 mL/participant within the trial prescribed procedures and will not exceed 275 mL for the entire study period (Appendix 3).

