5.5. Risk Benefit Evaluation for this Study

The administration of tafenoquine may be associated with unforeseen and serious risks.

Full discussions of the potential risks associated with the administration of tafenoquine are detailed in the Investigator's Brochure (60P IB).

No benefit is expected for individual participants participating in this study. Benefits of the study are society-based and related to possible future antimalarial therapies.

Risks to healthy (G6PD normal), participants in this study will be minimized in the following ways:

- Strict adherence to eligibility criteria will be maintained to ensure that only participants who are not at any perceived risk are enrolled in the study;
- The doses have been demonstrated previously to be safe and tolerable in healthy human participants and within predefined exposure limits;
- Close clinical monitoring to ensure the safety and well-being of the study participants including the following:
 - Exclusion of participants with clinically significant abnormalities from participation in the study at screening;
 - Regular measurements of participants' vital signs (blood pressure, pulse rate, sublingual temperature, respiratory rate);
 - Regular assessment of biochemistry and hematological blood parameters (including liver function tests) will be performed at scheduled time points and repeated, if necessary, to ensure appropriate follow-up of any clinically relevant abnormality.
- The total volume of blood drawn from each participant will not exceed 275 mL during the study ([Appendix 3](#)). This volume includes allowance for unscheduled safety laboratory assessments that may be required at the discretion of the PI to ensure participant safety.

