5.6. Route of Administration, Dosage Regimen, Treatment Period, and Justification

The 600 study participants will be randomized to the tafenoquine or the placebo group in a 1:1 ratio using clinical site as a randomization variable; two groups of 300 participants each will be enrolled in each group.

Each active IMP tablet will contain 100 mg tafenoquine. The dose to be administered orally is 200 mg tafenoquine (2 x 100 mg tablets) per day for three consecutive days (loading doses), followed by another 200 mg dose once per week for the following 51 weeks (beginning post-loading dose Day 10). The placebo group will receive identically-matched double-blind placebo tablets. The IMP tablets will be taken with 180 mL of water but there is no restriction on whether the tablets are taken with or without food.

Safety evaluations will include the following assessments: AE evaluation, physical examination, vital signs, laboratory parameters (hematology, biochemistry, and urinalysis). These will be performed at various time points throughout the study to assess baseline function and any changes from baseline after administration of IMP. Hematology, including methemoglobin assessment, biochemistry and urinalysis will be conducted at Screening, Weeks 4, 12, 24, 52, and 64. Clinical laboratory values indicative of an AE at EOS Week 64 will be repeated during the Follow-up Phase at Weeks 76, 89, 104 until resolution or stabilization.

Previous clinical studies support a recommended dosage tafenoquine regimen for malaria prophylaxis of a loading dose of 200 mg once daily for 3 days before travel to a malarious area, followed by weekly 200 mg maintenance doses while in the malarious area, for a period not exceeding 6 months, and an additional dose of 200 mg at one week of return from travel (60P IB).

In this study tafenoquine will be administered for 12 months to confirm the long term safety of tafenoquine past the 6-month safety window for travelers or military personnel who may be in a malarious area for prolonged periods of time.

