9.2.4. Laboratory Evaluations

Evaluations of standard laboratory parameters will be performed as part of the screening and baseline determinations of eligibility, as well as throughout the follow-up period as part of the safety assessments. Details of the timing of these evaluations are presented in [Section 1 Study Schedule of Events](#) and in [Section 8 Visit Schedule](#).

The investigator will document the clinical significance of all results falling outside of the normal reference ranges. All abnormal laboratory test results judged as being clinically significant by the investigator, will be reported to the LMM (and in turn the Data Safety Monitoring Board [DSMB]) and will be recorded as an AE. Repeated evaluations are

mandatory until normalization of the result(s) or until the change is no longer considered clinically significant.

Hematology

The following standard parameters will be assessed at all relevant time-points:

- RBC count, Hb, Hct, MCH, MCV, Plt count, WBC count with differential (neutrophils, lymphocytes, monocytes, eosinophils and basophils); and

A manual blood smear will be reviewed if immature/abnormal cells are detected on the automated differential or if an automated differential is not able to be performed

- MetHb %.

The methemoglobin assay is only performed at Clinipath's laboratory at the Mount Hospital (in Australia). Due to the short sample stability requirements, this sample must be routed/shipped to the Mount Hospital (or US equivalent laboratory) within 90 minutes of collection, to ensure analysis occurs within the 4-hour stability window period. An optical absorbance measurement will be taken using a Gem4000 analyzer (or equivalent). The Final Clinical Study Report (FCSR), will document the assay(s) used to measure methemoglobin.

Biochemistry

The following parameters will be measured at all relevant time-points:

- BUN, creatinine, potassium, sodium, AST, ALT, ALP, GGT, total and direct bilirubin.

Serology and other special laboratory investigations

- All participants will be screened for HBsAg, anti-HCV, anti-HIV-1 and anti-HIV-2 antibodies (if positive confirmed by a second test as per laboratory protocol).
- G6PD status will be determined at Screening.

Alcohol breath test, urine drug screen

- A urine screen for drugs of abuse (amphetamines, methamphetamines, barbiturates, benzodiazepines, cocaine, methadone, opiates, phencyclidine, tetrahydrocannabinols, and tricyclic antidepressants); and

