APPENDIX 3. ESTIMATE OF TOTAL BLOOD VOLUME COLLECTED DURING THE STUDY PERIOD

Note:

Total blood sampling volume for the individual participants participating in the study is approximately 135 mL.

The actual times of blood sampling may change. Additional blood samples may be taken for safety assessments as required by the PI or at times specified by the sponsor, provided the total volume taken during the study does not exceed 140 mL during the study including planned blood draws.

Procedure	Sample	Volume per sample (mL)	No. samples per participant	Total volume per participant (mL)
Laboratory test	G6PD testing	Blood volume for this sample will come from 4 mL hematology tube at screening		
	CBC	4	8	32
	MetHb%	4	7	28
	Biochemistry	5	7	35
	Serology	5	1	5
	Endocrinology (pregnancy)	5	2	10
Pharmacokinetic test	PK analysis	5	5	25
			TOTAL	135

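### The blood-volume ceiling per participant is 140 mL in Section 13.1 and Appendix 3 but 275 mL in the Synopsis and Section 5.5, and 140 mL is too small for the repeat tests some participants would need.

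*Combined protocol and SAP*

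**What the plan says.** Four places in the current protocol text limit the total blood drawn from one participant.

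- **Synopsis**, end of the assessments section: scheduled sampling is estimated at 135 mL, and the total "will not exceed 275 mL for the entire study period". It cites Appendix 3.
- **Section 5.5**: "The total volume of blood drawn from each participant will not exceed 275 mL during the study". It also cites Appendix 3 and adds: "This volume includes allowance for unscheduled safety laboratory assessments that may be required at the discretion of the PI".
- **Section 13.1**: "The maximum amount of blood to be collected from an individual over the entire study period is approximately 135 mL". The next paragraph permits additional safety samples if the total "does not exceed 140 mL during the study period".
- **Appendix 3**: a planned total of about 135 mL, with further samples allowed "provided the total volume taken during the study does not exceed 140 mL". The same sentence states that scheduled draws count toward that figure.

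Two other sections call for further blood. Under Section 9.2.4, repeat evaluations of clinically significant laboratory results are "mandatory until normalization of the result(s) or until the change is no longer considered clinically significant". Section 5.6 states: "Clinical laboratory values indicative of an AE at EOS Week 64 will be repeated during the Follow-up Phase at Weeks 76, 89, 104", continuing until the finding resolves or stabilizes. Section 8.5 makes Part 3 blood sampling conditional on there being an abnormality to follow.

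**The concern.** A ceiling on blood volume is an operative safety limit, and sites need to know which figure binds. The two sections that give 275 mL refer to an appendix that says 140 mL, so following the cross-reference does not settle the matter.

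The lower figure also conflicts with the protocol's own follow-up rules. It sits just above the scheduled volume, while mandatory repeats and up to three Part 3 visits can add several tubes. A site working to 140 mL could not complete required safety follow-up in some participants. A site working to 275 mL that passed 140 mL would deviate from Section 13.1. These needs are foreseeable: Section 5.5.1.2 lists methemoglobinemia as an observed effect, and Section 10.11.1 makes methemoglobin above 10% and several liver-test elevations events of special interest.

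Section 13.1 also calls 135 mL a maximum, although the Synopsis and Appendix 3 treat it as the scheduled volume and the next paragraph of Section 13.1 goes beyond it.

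**Working it through.** **1. Reproduce the planned volume (Appendix 3, volume per sample × number of samples).**

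| Sample | mL | Number | Total (mL) |
|---|---|---|---|
| CBC | 4 | 8 | 32 |
| MetHb | 4 | 7 | 28 |
| Biochemistry | 5 | 7 | 35 |
| Serology | 5 | 1 | 5 |
| Pregnancy | 5 | 2 | 10 |
| PK | 5 | 5 | 25 |

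Sum: 32 + 28 + 35 + 5 + 10 + 25 = 135 mL, as stated.

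**2. Room above the plan.** Under the lower ceiling, 140 − 135 = 5 mL. Under the higher, 275 − 135 = 140 mL.

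**3. Full repeat panel.** CBC 4 + MetHb 4 + biochemistry 5 = 13 mL. Three panels correspond to one at each of Weeks 76, 89 and 104.

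**4. Totals under different bases.** The base depends on how many serum pregnancy or FSH tubes are drawn (0, 1 or 2) and on whether 8 CBCs (Appendix 3) or 7 (the hematology time points in the Section 1 schedule) are counted.

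| Pregnancy/FSH tubes | CBCs | Base (mL) | +1 panel | +2 panels | +3 panels |
|---|---|---|---|---|---|
| 2 | 8 | 135 | 148 | 161 | 174 |
| 2 | 7 | 131 | 144 | 157 | 170 |
| 1 | 8 | 130 | 143 | 156 | 169 |
| 1 | 7 | 126 | 139 | 152 | 165 |
| 0 | 8 | 125 | 138 | 151 | 164 |
| 0 | 7 | 121 | 134 | 147 | 160 |

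The second full panel exceeds 140 mL in every row. After three panels the excess is 160 − 140 = 20 mL to 174 − 140 = 34 mL. Under 275 mL, between 275 − 174 = 101 mL and 275 − 160 = 115 mL would remain.

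**5. Smaller repeats.**

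- One test repeated once, from 135 mL: CBC or MetHb gives 139 mL and biochemistry gives 140 mL. Both fit.
- From 135 mL, two MetHb repeats give 143 mL, two biochemistry repeats 145 mL, and one CBC plus one biochemistry 144 mL. All exceed 140 mL.
- One test repeated at all three Part 3 visits, from 135 mL: 135 + 3×4 = 147 mL for CBC or MetHb, and 135 + 3×5 = 150 mL for biochemistry. From 125 mL (no pregnancy tubes): 137 and 140 mL, which fit.

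**6. Can the two ceilings be reconciled?** Because 135 + 140 = 275, the 140 mL may have begun as an allowance on top of the plan. That is only an inference. Section 13.1 and Appendix 3 both apply 140 mL to the total, and Appendix 3 counts scheduled draws within it, so the text as written excludes this reading.

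**The case against.** The strongest reply accepts the conflict and disputes its size. Part 3 draws are limited to what is needed to follow the abnormality, so the full-panel figures are a worst case. A man with one abnormal test repeated at all three visits reaches 137 to 140 mL and stays within the lower ceiling. Section 9.2.4 sets no interval for repeats, so scheduled visits already counted in the 135 mL may serve as some of them. Unscheduled draws under Section 8.7 are discretionary, and Section 10.2 gives the investigator authority to do whatever safety requires, so in practice a needed sample would be taken and recorded as a deviation.

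Much of this stands. The 20 to 34 mL excess applies to three full panels, not to a typical participant, and one single-tube repeat always fits. It does not remove the problem. A woman with both serum pregnancy tubes and one abnormal test followed through Part 3 reaches 147 to 150 mL. A limit that must be breached to carry out required follow-up is wrongly set. No reading makes 140 mL and 275 mL the same ceiling.

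Two side points are also fair. The Appendix 3 sum is correct, so the fault is inconsistency between sections. The eighth CBC is worth only 4 mL and may be an allowance, since Section 8.1 permits a laboratory repeat at screening.

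**Conclusion.** The concern holds and should be corrected. One quantity has two ceilings 135 mL apart (275 − 140) in current text. The lower one fails by the second full repeat panel on every base considered, and sooner for participants on the 135 mL base. It affects only participants with laboratory findings that need more than a few extra tubes.

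The figures rest on the Appendix 3 tube volumes and on Part 3 draws counting toward the study total. The documents reviewed do not show which ceiling the ethics committees approved or what the consent form states.

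This is a participant-protection and compliance matter. It has no bearing on the primary endpoint, the power or the analysis.

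**What to change.** - In Section 13.1 and Appendix 3, replace 140 mL with 275 mL, the ceiling that Section 5.5 already describes as covering unscheduled safety draws. If the ethics committees approved a different single ceiling, use it in all four places, provided it is at least about 175 mL (the 174 mL worst case above, rounded up) plus an allowance for unscheduled draws.
- In Section 13.1, describe 135 mL as the planned volume, not the maximum.
- In Appendix 3, explain the eighth CBC sample or reduce it to the seven scheduled time points. With seven, the planned total becomes 135 − 4 = 131 mL.
- Check that the consent form states the same ceiling.

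The cost is wording in two places, the consent check, and submission of the amendment to the ethics bodies under Section 13.2. Procedures, sample size and analysis do not change.

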13.2. Ethical Review

The protocol, consent forms and participant information sheets will be reviewed by the Bellberry-HREC, US IRB and HRPO. No study activities will be initiated prior to the approval of these documents by these committees. All amendments and addenda to the protocol will similarly be submitted to the Bellberry-HREC, IRB and HRPO for approval prior to their implementation.

13.3. Informed Consent Procedures

Participants will be fully informed of the nature of the study, the properties and side effects of the IMP and all relevant aspects of study procedures in the participant information sheet and informed consent document. The nature of the study, the IMP and its side effects will also be discussed with the participants by the investigator during recruitment. The participants may ask questions of the investigator or the clinic staff at any time.

The 'Informed Consent' form will be signed and dated by the participants in the presence of an investigator. Participants will also be given a copy of their signed 'Informed Consent' form.

In the event that the sponsor wants to perform testing on the samples that is not described in this protocol, additional HREC/IRB approval will be sought.

13.4. Subject Data Protection

Participants will be informed that their data will be held on file by the Study Site and that these data may be viewed by staff of the Australian Local Sponsor who are responsible for monitoring the study according to [ICH GCP](#) and by the local US FDA.

Upon request, the investigator(s)/institution(s) will permit direct access to source data/documents for trial-related monitoring, audits, HREC/IRB and HRPO review, and regulatory inspection(s) by the sponsor (or their appropriately qualified delegates) and Regulatory Authorities. Direct access includes examination, analysis, verification and reproduction of records and reports that are important to the evaluation of the trial.

They will similarly be informed that a report of the study will be submitted to the sponsor company and may also be submitted to government agencies in Australia and overseas and perhaps for publication, but that they will only be identified in such reports by their study identification number, initials and perhaps their gender and age. The investigators undertake to hold all personal information in confidence.

14. ADMINISTRATIVE CONSIDERATIONS

14.1. Liability/Indemnity/Insurance

The study sponsor will ensure sufficient insurance is available to enable it to indemnify and hold the investigator(s) and relevant staff as well as any hospital, institution, HREC/IRB or the like, harmless from any claims for damages for unexpected injuries, including death, that may be caused by the participant's participation in the study but only to the extent that the claim is not caused by the fault or negligence of the participants or investigator(s). The sponsor adheres to the guidelines of Medicines Australia for injury resulting from participation in a company-sponsored trial, including the provision of "no-fault clinical trial insurance" ([Medicines Australia 2016](#)).

14.2. Changes to the Final Study Protocol

Changes to the final study protocol can only be made with the prior consent of the sponsor and the HREC/IRB/HRPO. All such changes must be attached to, or incorporated into, the final protocol, and communicated to all relevant members of the Study Site staff and, if appropriate, to trial participants. All deviations from this study protocol will be reported on eCRFs and will be included in the trial master file and included in the FCSR. An assessment of the significance of each protocol deviation will be given in the FCSR. All deviations/amendments will be reported to sponsor.

14.2.1. Non-Substantial Amendment

Administrative or logistical minor changes to the protocol require a non-substantial amendment. Such changes include but are not limited to changes in study staff or contact details (e.g., sponsor instead of CRO monitors) or minor changes in the packaging or labeling of the IMP. An amendment deemed to be non-substantial must have no ethical implications.

The implementation of a non-substantial amendment may be done without notification to HRPO. However, the HREC/IRB will receive notification of non-substantial amendments.

14.2.2. Substantial Amendment

Significant changes to the protocol require a substantial amendment. Significant changes include but are not limited to: new data affecting the safety of participants, change to the objectives/endpoints of the study, the eligibility criteria, dose regimen, study assessments/procedures, treatment or study duration, with or without the need to modify the participant information sheet and informed consent.

Substantial amendments are to be approved by the HREC/IRB/HRPO. For HRPO purposes, substantial amendments may also include a change in the PI, change or addition of an institution, change to the HREC/IRB of Record, elimination or alteration of the consent process, change to the study that has regulatory implications, significant changes in the study design that would prompt additional scientific review or a change that could potentially increase risk to participants. The implementation of a substantial amendment can only occur after formal approval by the HREC/IRB /HRPO and must be signed by the PI.

14.2.3. Urgent Amendment

An urgent amendment might become necessary to preserve the safety of the participants enrolled in the study. The requirements for approval should in no way prevent any immediate action being taken by the investigators or the sponsor that is in the best interests of the participants. Therefore, if deemed necessary, an investigator can implement an immediate change to the protocol for safety reasons. This means that, exceptionally, the implementation of urgent amendments will occur before submission to and approval by the HREC/IRB /HRPO.

In such cases, the investigator must notify the sponsor within 24 hours of implementation of the amendment. A related substantial amendment will be written within 10 working days and submitted to the HREC/IRB /HRPO, together with a description of the steps, which have already been taken regarding implementation of this amendment.

